2. PROTOCOL SUMMARY FOR STUDY RVT-1401-2003

Study Title	A Phase 2, Multicenter, Non-Randomized, Open-Label Study of RVT-1401 for the Treatment of Patients with Warm Autoimmune Hemolytic Anemia
Objectives	
Primary
 
To examine the effect of RVT-1401 on proportion of responders (defined as Hb level ≥ 10g/dL with at least a ≥ 2 g/dL increase from baseline without rescue therapy or blood transfusions in the previous two weeks)
 
To assess the safety and tolerability of RVT-1401 in subjects with WAIHA
 
Secondary
 
To examine the effect of RVT-1401 on change in Hb levels
 
To examine the effect of RVT-1401 on time to response
 
To examine the effect of RVT-1401 on change in hematocrit levels
 
To examine the effect of RVT-1401 on proportion of participants with Hb levels in the normal range
 
To examine the effect of RVT-1401 on time to achieving Hb levels in the normal range
 
To examine the effect of RVT-1401 on change in fatigue
 
To examine the effect of RVT-1401 on change in dyspnea
 
To examine the effect of RVT-1401 on change in health-related quality of life
 
To assess the change in serum levels of total IgG & IgG subclasses (I-IV)
 
To examine RVT-1401 PK following repeated doses in patients with WAIHA
 
To assess the changes in LDH, bilirubin, haptoglobin
 
To measure anti-RVT-1401 antibodies following repeated doses in patients with WAIHA

Study Phase	Phase 2
Target Population	Warm Autoimmune Hemolytic Anemia

Number of Participants Planned	Approximately 16 participants
Number of Study Centers Planned	Approximately 22 centers
Study Design	Non-randomized, open-label study to investigate the efficacy, safety and tolerability of RVT-1401
Duration of Treatment	12 weeks
Criteria for Evaluation (Endpoints)	
Primary
 
Proportion of responders at week 13
 
Assessment of safety and tolerability by analysis of adverse event (AE) data and changes from baseline in vital signs, ECGs, and clinical laboratory values
 
Secondary
 
Change from baseline in Hb levels
 
Time to response
 
Change from baseline in hematocrit levels
 
Proportion of participants with Hb levels in the normal range at week 13
 
Time to achieving Hb levels in the normal range
 
Change from baseline in FACIT-F score
 
Change from baseline in Medical Research Council (MRC) breathlessness scale
 
Change from baseline in EQ-5D-3L score
 
Change from baseline in levels of total IgG & IgG subclasses (I-IV)
 
Concentration of RVT-1401 pre-dose (Ctrough)
 
Change from baseline in LDH, bilirubin, and haptoglobin
 
Immunogenicity determined by change from pre-dose in anti-RVT-1401 antibodies, and characterization of any anti-RVT-1401 to confirm neutralization potential

3. INTRODUCTION

3.1. Background

RVT 1401 is a fully human anti-neonatal Fc receptor (FcRn) monoclonal antibody. FcRn is critical to the regulation of immunoglobulin G (IgG) [Roopenian, 2007]. In addition to its central role in mediating the transport of IgG within and across cells of diverse origin, it also serves to rescue IgG from degradation, thereby prolonging its circulating half-life [Roopenian, 2007]. Targeting the FcRn pathway has been shown to dramatically reduce circulating IgG, including auto-antibodies (Ab) of the IgG subclass, thus supporting its use in the treatment of auto-Ab mediated autoimmune diseases. RVT-1401 functions by inhibiting the binding of IgG to FcRn, resulting in the rapid catabolism of IgG via lysosomal degradation.

3.2. Warm Autoimmune Hemolytic Anemia

Autoimmune hemolytic anemia (AIHA) is caused by increased red blood cell (RBC) destruction triggered by autoantibodies that react against RBC antigens with or without complement. Antibodies in warm autoimmune hemolytic anemia (WAIHA) react optimally at 37 degrees Celsius and is the most common type of AIHA, comprising approximately 70-80% of all adult cases [Sokol, 1981]. The most common antibody isotype involved in WAIHA is IgG, with a greater prevalence of IgG1 and IgG3 [Kalfa, 2016]. Intravascular destruction of RBCs through complement mediated mechanisms contributes in only a minor percentage of WAIHA patients. In most patients, erythrocytes coated by warm reacting IgG are bound by spleen macrophages via FcR, which causes them to be either phagocytosed or have part of their membrane removed in the spleen. In the latter case they form microspherocytes that are then subject to further destruction during their next passage through the spleen [Kalfa, 2016]. CD8⁺ T cells, and natural killer (NK cells) may also contribute to RBC lysis through antibody dependent cell mediated cytotoxicity (ADCC). RVT-1401, by reducing the levels of anti-RBC IgG, is hypothesized to be effective for the treatment of patients with WAIHA.

The clinical presentation of WAIHA is characterized by fatigue, exertional dyspnea, pallor, and splenomegaly. Common laboratory findings include: decreased hemoglobin (Hb), reticulocytosis, elevated unconjugated bilirubin and lactate dehydrogenase, serum aspartate aminotransferase disproportionately higher than serum alanine aminotransferase, and decreased haptoglobin [Kalfa, 2016].

Based on a paucity of phase 3 trials, the treatment of WAIHA is primarily guided by retrospective reviews, case series, expert opinions and a few small phase 2 trials. Nevertheless, Kalfa, et al, conclude that available evidence demonstrates that WAIHA can be fatal due to an acute presentation or due to refractory disease in spite of multiple lines of therapy. [Kalfa, 2016]. Experts recommend initial treatment with high dose steroids (60-100mg/day) and note that most patients will respond to these doses. Experts also recommend steroid taper after patients respond, due to toxicity of steroids at this high dose. Patients with worsening disease as steroids are tapered are candidates for further lines of therapy with immunosuppressants. Finally, although transfusions are generally reserved for stabilizing patients in the acute phase of WAIHA, some patients

require chronic transfusions due to WAIHA that is refractory to prednisone and or immunosuppressants. [Jaeger, 2019]

3.3. Rationale

3.3.1. Study Rationale

The purpose of the current study is to assess the efficacy and safety of RVT-1401 in the treatment of WAIHA that is worsening or refractory in spite of therapy with steroids and or immunosuppressants or worsening with steroid or immunosuppressant taper. Results from this study will be used to inform dosing and to support progression into a Phase 3 study.

3.3.2. Dose rationale

Two dosing regimens of RVT-1401 will be assessed in this non-randomized open label study. Both will involve once weekly subcutaneous (SC) injections:

- Dosing Regimen A -680 mg weekly for 12 weeks, and
- Dosing Regimen B - 340 mg weekly for 12 weeks

[figure not shown]
Given that there is a practical limit on the volume that can be administered via SC injection, these two doses represent what can be administered as a single SC injection (340 mg) and two SC injections (680 mg) per week with the current formulation.

Expected Treatment Effect

The proposed dosing regimens are expected to provide a sustained total IgG reduction of approximately 75-80% and 65-70% for Regimen A and B respectively. It is expected that the nadir IgG reduction will be achieved by the 3rd-5th dose (depending on dose studied) and maintained following the remaining doses before rising back to baseline over the next 6 to 8 weeks after stopping treatment.

These assumptions are supported by preliminary pharmacodynamic (PD) results, shown in Figure 1, from the Phase 1 clinical study RVT-1401-1001 (Section 3.3.3). Dosing regimen A (weekly 680 mg) represents the dose that is expected to achieve the maximal effect in IgG reduction. In healthy participants, 4 weekly SC injections of 680 mg of RVT-1401 produced the maximum PD response with an average total IgG percent reduction from baseline of 78%. This effect occurred prior to the 4th dose and no further reduction was observed after dosing, indicating maximal reduction and steady state response had been achieved. In the 340 mg repeat dose cohort, there were some individuals who did not achieve nadir IgG concentration until after the last dose, indicating they may have not reached steady state. Data from this study will be used to support dose selection in future studies.

Figure 1: Mean(+/-SD) Serum IgG Reduction Following Multiple SC Doses of RVT-1401

3.3.3. Clinical Experience

Two Phase 1 clinical studies to assess safety, tolerability, pharmacokinetics (PK), and PD have been conducted in healthy volunteers under the RVT-1401 clinical development program. A total of 99 healthy subjects participated in these two studies, 77 of whom received at least 1 dose of RVT-1401. Table 1 summarizes the doses of RVT-1401 administered in healthy subjects. The dosing and recovery phase of these two studies have been completed and the study reports are being finalized. Three additional studies are ongoing, investigating RVT-1401 use in Graves’ Ophthalmopathy and myasthenia gravis.

Refer to Investigator’s brochure (IB) for additional information on clinical experience with RVT-1401.

Table 1: RVT-1401 Doses in Healthy Subjects

RVT-1401 Dose	Duration	Healthy Subjects
0.1 mg/kg	Single 1 hr IV Infusion	4
0.5 mg/kg	Single SC injection	3
1.5 mg/kg	Single SC injection	6
5.0 mg/kg	Single SC injection	6
340 mg	Single SC injection	6
500 mg	Single SC injection	6
765 mg	Single SC injection	6
100 mg	Single 1 hr IV Infusion	6
340 mg	Single 1 hr IV Infusion	6
765 mg	Single 1 hr IV Infusion	6
1530 mg	Single 1 hr IV Infusion	6
340 mg	4 weeks of once weekly SC injections*	8
680 mg	4 weeks of once weekly SC injections	8
Total for All Studies		77

Abbreviations: IV, Intravenous; SC, subcutaneous

* Note: 1 subject received 3 weeks and 1 subject received 2 weeks of once weekly SC injections

3.3.3.1. Safety

See Investigator's Brochure for details.

[figure not shown]
RVT-1401 has been well tolerated with no Grade 3 or 4 adverse events (AEs), and no withdrawals due to AEs. There have been two serious adverse events (SAEs) (Malpighian carcinoma in left side of the neck and appendicitis) considered unrelated to study drug.

All other AEs in subjects receiving RVT-1401 have been reported as mild or moderate.

The most frequently reported AE was injection site reactions (erythema and/or swelling). The rate of injection site reactions was similar between RVT-1401-treated and placebo-treated subjects and was not dose-related. Injection site reactions have generally resolved within a few hours after dosing; there were two exceptions of mild swelling (one RVT-1401- and one placebo-treated subject) that resolved after 3 and 4 days, respectively. Additionally, injection site reactions were not consistently observed following every injection in the repeat dose cohorts.

Preliminary data suggest no subject who has received RVT-1401 had clinically relevant changes in vital signs or laboratory results, or on electrocardiogram (ECG).

3.3.3.2. Pharmacokinetics

[figure not shown]
3.3.3.3. Pharmacodynamics

Following the administration of single SC doses of RVT-1401, total IgG reduction increased with increasing dose, with a maximum reduction of 47% observed after a fixed dose of 765 mg. The nadir for IgG reduction following single SC dosing occurred between days 8-15 in most individuals. IgG serum levels on average returned to within 90% of baseline by 43 days after drug administration. Albumin levels were also reduced from baseline when compared to placebo showing a similar dose related trend. The highest albumin reductions occurred following the 765 mg SC dose ([REDACTED]) but were not considered to be clinically significant reductions as all patients remained within normal limits (3.5 g/dL to 5.5 g/dL) and levels recovered quickly, returning to baseline ~ 2 weeks after nadir.

The amount of IgG reduction has also been assessed following weekly SC administration of 340 and 680 mg of RVT-1401 or placebo for 4 weeks. There were 8 and 7 subjects with data included in the preliminary PD analysis for the 680 mg and 340 mg cohorts respectively. Data from one subject who received 2 doses of 340 mg prior to early study withdrawal due to personal reasons was not included. Across the two cohorts, there were 4 subjects who received placebo with data that contributed to the analysis of PD endpoints. Figure 1 presents the mean IgG concentration-time profiles, as a percent of

pre-dose, for both weekly SC administration of 340 mg and 680 mg doses. While both 340 mg and 680 mg cohorts showed a reduction in serum IgG, the placebo group demonstrated minimal changes in serum IgG. The reduction in serum IgG was more rapid following the 680 mg SC compared with 340 mg SC. The median IgG nadir concentration occurred prior to the last dose in the 680 mg cohort whereas for 340 mg, it occurred approximately 3 days after the last dose. The finding that the 680 mg cohort achieved nadir concentration following the 3rd dose and maintained serum IgG reduction after the 4th dose, indicates a maximum response has likely been achieved, and that higher doses or more frequent dosing would yield little additional benefit. This is consistent with data from other anti-FcRn agents in development that have observed a maximum percent reduction in serum IgG from baseline of ~ 75-80% [Howard, 2019; Kiessling, 2017; Ling, 2018].

Preliminary data following the last dose across both cohorts shows that IgG levels were within normal range and within 30% of the baseline value by 5 weeks after the last dose (average (SD) IgG concentration was 8.64 (2.73) g/L, and 8.95 (2.03) g/L for the 340 mg and 680 mg cohorts, respectively). The return towards baseline indicates the effect of RVT-1401 is reversible.

Additional information is available in the current Investigator's Brochure.

3.4. Benefit: Risk Assessment

Summaries of findings from both clinical and non-clinical studies conducted with RVT-1401 can be found in the current IB.

[figure not shown]
3.4.1. Risk Assessment

Potential Risk of Clinical Significance	Mitigation Strategy	
	Impact on Eligibility	Monitoring and Stopping Criteria OR Management Criteria
The potential for allergic reactions exists following administration of any protein to human participants.	Participants with history of anaphylaxis (i.e., serious, life-threatening allergic reactions) are ineligible.	Participants will be closely monitored for reactions for 30 min post-dose.
Changes in circulating complement	None	Serum complement will be monitored throughout the study (Section 8.1). Abnormal values will be discussed with the study medical monitor.
Sustained hypogammaglobulinemia	
The following participants will be ineligible:
 
 -Participants with a total IgG level of <6g/L at screening -Participant has a past medical history of primary immunodeficiency, T-cell or humoral, including common variable immunodeficiency. -History of or known infection with human immunodeficiency virus (HIV), hepatitis B virus (HBV), or Mycobacterium tuberculosis: 
 - Participants must have negative test results for HBV surface antigen, HBV core antibody, HIV 1 and 2 antibodies, and a negative QuantiFERON-TB Gold test at Screening. - Hepatitis C virus (HCV): 
 - Participants must have a negative test result for HCV antibody or - Participants with a known history of HCV must have documented evidence of sustained virologic response that is consistent with cure of hepatitis C infection that is 	Total IgG levels will be monitored throughout the study (Section 8.1).

	
confirmed with a negative HCV RNA test at Screening.
 
-Absolute neutrophil count <1000 cells/mm³
	

Sustained hypoalbuminemia
	
Participants with baseline albumin levels <3.5 g/dL will be ineligible.
 
Subjects with advanced liver disease including any diagnosis of cirrhosis of any stage will be ineligible.
 
Non-alcoholic fatty liver disease (NAFLD) including non-alcoholic steatohepatitis (NASH) is allowable if there has been a recent (within 6 months) normal ultrasound, CT, or MRI. If the ultrasound, CT, or MRI demonstrate fatty changes alone, the subject may be enrolled if s/he has a normal range fibroscan for liver fibrosis.
 
AST or ALT $\geq 1.5 \times$ ULN at Screening. The subject may only be enrolled if s/he has a recent (within 6 months) normal ultrasound, CT, or MRI. If the ultrasound, CT, or MRI demonstrate fatty changes alone, the subject may be enrolled if s/he has a normal range fibroscan for liver fibrosis.
	
Serum albumin levels will be monitored throughout the study (Section 8.1). Criteria that would require dose interruption and/or discontinuation for Grade 2 and Grade 3 albumin levels have been added (Section 6.8.3).

4. OBJECTIVE(S) AND ENDPOINT(S)

Objectives	Endpoints
Primary	

To examine the effect of RVT-1401 on proportion of responders (defined as Hb level $\geq 10\text{g/dL}$ with at least a $\geq 2\text{ g/dL}$ increase from baseline without rescue therapy or blood transfusions in the previous two weeks)
 
To assess the safety and tolerability of RVT-1401 in subjects with WAIHA
	
Proportion of responders at week 13
 
Assessment of safety and tolerability by analysis of adverse event (AE) data and changes from baseline in vital signs, ECGs, and clinical laboratory values

Secondary	

To examine the effect of RVT-1401 on change in Hb levels
	
Change from baseline in Hb levels

To examine the effect of RVT-1401 on time to response
	
Time to response

To examine the effect of RVT-1401 on change in hematocrit levels
	
Change from baseline in hematocrit levels

To examine the effect of RVT-1401 on proportion of participants with Hb levels in the normal range
	
Proportion of participants with Hb levels in the normal range at week 13

To examine the effect of RVT-1401 on time to achieving Hb levels in the normal range
	
Time to achieving Hb levels in the normal range

To examine the effect of RVT-1401 on change in fatigue
	
Change from baseline in FACIT-F score

To examine the effect of RVT-1401 on change in dyspnea
	
Change from baseline in Medical Research Council (MRC) breathlessness scale

To examine the effect of RVT-1401 on change in health-related quality of life
	
Change from baseline in EQ-5D-3L score

To assess the change in serum levels of total IgG & IgG subclasses (I-IV)
	
Change from baseline in levels of total IgG & IgG subclasses (I-IV)

To examine RVT-1401 PK following repeated doses in patients with WAIHA
	
Concentration of RVT-1401 pre-dose (C_{trough})

To assess the changes in LDH, bilirubin,
	
Change from baseline in LDH, bilirubin, and

haptoglobin
 
To measure anti-RVT-1401 antibodies following repeated doses in patients with WAIHA
	
haptoglobin
 
Immunogenicity determined by change from pre-dose in anti-RVT-1401 antibodies, and characterization of any anti-RVT-1401 to confirm neutralization potential

Exploratory
	
	

5. STUDY DESIGN

5.1. Overall Design

This is a Phase 2, non-randomized, sequential, open-label study to investigate the safety, tolerability, PK, PD, and efficacy of RVT-1401 (680 mg/weekly and 340 mg/weekly) in patients with WAIHA. The study design is illustrated in Section 5.2.

[figure not shown]
Two cohorts of participants will be enrolled in a non-randomized sequential approach. Participants will be enrolled into Cohort 1 (680 mg/weekly) first followed by Cohort 2 (340 mg/weekly). In the Phase I healthy volunteer study, both dosing regimens were well tolerated (Section 3.3.3). Since 680 mg/weekly has the greater likelihood of demonstrating clinical efficacy, this dosing regimen will be studied in Cohort 1.

Following the initial dose at the Baseline Visit (Week 1, Day 1), study visits will occur weekly throughout the treatment period. Following the final dose at Week 12, visits will occur weekly through Week 14 and then at Week 16 and Week 20. Safety, PK, PD, and clinical assessments will be collected throughout the study. Refer to Section 8.1, Time and Events Table.

Optional home visits will be offered to collect (at a minimum) blood samples, vital signs, and to review adverse events and concomitant medications.

Each participant will participate in the study for up to approximately 24 weeks: up to a 4-week screening period, a 12-week treatment period, and an 8-week follow up period.

5.2. Study Schematic

**Note-Cohort 1 will enroll first followed by Cohort 2

5.3. Treatment Arms and Duration

Participants will receive RVT-1401 for 12 weeks (680 mg/weekly or 340 mg/weekly).

6. PARTICIPANT POPULATION

6.1. Type and Number of Participants

A sufficient number of participants will be enrolled to achieve approximately 16 evaluable participants. Enrollment is competitive.

In order to manage the total study enrollment, the Sponsor may suspend screening and/or enrollment at any site or study-wide at any time.

If participants prematurely discontinue the study, additional replacement participants may be enrolled at the discretion of the Sponsor.

Deviations from inclusion and exclusion criteria are not allowed because they can potentially jeopardize the scientific integrity of the study, regulatory acceptability or participant safety. Therefore, adherence to the criteria as specified in the protocol is essential.

To determine participant eligibility at screening, a single repeat of certain tests such as laboratory values or ECGs is allowed at the discretion of the Principal Investigator.

6.2. Inclusion Criteria

A participant will be eligible for inclusion in this study only if all of the following criteria apply:

1. Male or female ≥ 18 years of age.
2. Diagnosis of primary or secondary WAIHA as documented by a positive direct antiglobulin test (DAT) specific for anti-IgG alone or anti-IgG plus C3d.
3. Secondary WAIHA may only include Stage 0 chronic lymphocytic leukemia (CLL) in which separate treatment is not indicated, nor anticipated to require active management for the duration of the study.
4. Have failed or not tolerated at least one prior WAIHA treatment regimen as per local standards (e.g., steroids, rituximab, azathioprine, cyclophosphamide, cyclosporine, mycophenolate mofetil (MMF), danazol, or vincristine). Failure is defined as worsening or refractory disease despite steroids and or immunosuppressants.
5. Participants with splenectomy ≥ 3 months from Day 1 who are up to date on vaccinations (based on age and local guidance) are allowed.
6. Haptoglobin $<$ lower limit of normal (LLN) and lactate dehydrogenase (LDH) $>$ upper limit of normal (ULN).
7. At Screening and Baseline, subject's hemoglobin level must be < 10 g/dL and the subject must have documented symptoms related to anemia (e.g., weakness, dizziness, fatigue, shortness of breath, chest pain).
8. Karnofsky Performance status ≥ 60 .
9. Subject's concurrent treatment for WAIHA may consist only of steroids (stable dose for at least two weeks prior to Day 1), immunosuppressant therapy (azathioprine, MMF, or cyclosporine) that has been at a stable dose for at least four weeks prior to Day 1, or erythropoietin (stable dose for at least 6 weeks prior to Day 1). [Note: starting doses of WAIHA therapy must be maintained throughout the study except in the case of a rescue medication as per local standards for safety. Steroid taper down to 10 mg/day will be allowed for participants who achieve response for at least 2 weeks.]
10. A female participant is eligible to participate if she is of:
 - a. Non-childbearing potential defined as pre-menopausal females with a documented bilateral tubal ligation, bilateral oophorectomy (removal of the ovaries) or hysterectomy; hysteroscopic sterilization, or postmenopausal defined as 12 months of spontaneous amenorrhea [in questionable cases a blood sample with simultaneous follicle stimulating hormone (FSH) in the post-menopausal range is confirmatory].
 - b. Child-bearing potential and agrees to use one of the contraception methods listed in Section 6.6.1 for an appropriate period of time (as determined by the product label or Principal Investigator) prior to the start of dosing to sufficiently minimize the risk of pregnancy at that point. Female participants must agree to use contraception until 90 days after the last dose of study treatment.

11. Male participants must agree to use one of the contraception methods listed in Section 6.6.1. This criterion must be followed from the time of the first dose of study treatment until 90 days after the last dose of study treatment.
12. Willing and capable of giving written informed consent, which includes compliance with the requirements and restrictions listed in the consent form.

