6.7. Withdrawal Criteria

6.7.1. Reasons for Withdrawal

A Principal Investigator may discontinue/withdraw a participant from the study if any of the following criteria apply:

- Any clinical AE, laboratory abnormality, or other medical condition or situation occurs such that continued participation in the study would not be in the best interest of the participant.
- Participant pregnancy
- Significant protocol violation (e.g., non-compliance with concomitant medications)
- Behavioral or administrative issue
- Participant request to discontinue/withdraw consent for any reason. It is important to document whether the withdrawal of consent is primarily due to an AE, lack of efficacy, or other reason.
- Discontinuation of the study at the request of the Sponsor, regulatory agency or an Institutional Review Board (IRB)/ Independent Ethics Committee (IEC)
- Stopping criteria, as noted in Section 6.8

If a participant meets a withdrawal criterion during treatment, an Early Termination visit will be required (Section 6.7.2).

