6.9.2. Management of Rescue Therapy

Rescue therapy during the first 8 weeks of the Treatment Period is permitted for participants with haemoglobin levels <7.0 g/dL or in the presence of signs/symptoms of myocardial ischemia, hypoxia, or TIA/stroke. Participants requiring rescue therapy after the Week 8 visit will be discontinued and an early withdrawal visit scheduled.

Blood Transfusion

The date, time, and number of units transfused should be recorded, along with the results of cross-match testing. Follow-up hemoglobin should be measured with 12 hours of the end of the transfusion. Hemoglobin values will be censored from efficacy analyses for the 2 weeks following a blood transfusion.

Prednisone/Prednisolone

Prednisone/prednisolone rescue (up to a 50% increase from baseline for up to 5 days), is permitted as per the rescue therapy guidelines (Section 6.9.2). The date, time, and dose should be recorded. Hemoglobin values will be censored from efficacy analyses for the 2 weeks following the last dose of prednisone/prednisolone rescue.

Dexamethasone

High dose dexamethasone (up to 40 mg daily for up to 4 days) is permitted as per the rescue therapy guidelines (Section 6.9.2). The date, time, and dose should be recorded. Hemoglobin values will be censored from efficacy analyses for the 2 weeks following the last dose of dexamethasone rescue.

IVIg and Plasma Exchange

Due to the mechanism of action for RVT-1401, the use of IVIG and Plasma exchange are not allowed.

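### The Week 13 responder rule does not cover a non-permitted, longer-acting WAIHA therapy completed by about Week 8, and the inclusion 9 note on rescue is looser than Section 6.9.2

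*Protocol*

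**What the plan says.** **Background therapy and rescue.** Protocol Section 6.2, criterion 9, states that "concurrent treatment for WAIHA may consist only of steroids", or certain stable-dose immunosuppressants, or erythropoietin. Its note adds that "starting doses of WAIHA therapy must be maintained throughout the study except in the case of a rescue medication as per local standards for safety". The note gives no agent, dose or time limit and does not refer to Section 6.9.2.

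**Rescue rules (Protocol Section 6.9.2).**
- Trigger and timing: "Rescue therapy during the first 8 weeks of the Treatment Period is permitted for participants with haemoglobin levels <7.0 g/dL", or for signs of myocardial ischemia, hypoxia or TIA/stroke.
- Steroids: "Prednisone/prednisolone rescue (up to a 50% increase from baseline for up to 5 days), is permitted", and "High dose dexamethasone (up to 40 mg daily for up to 4 days) is permitted".
- Banned: "the use of IVIG and Plasma exchange are not allowed".
- After Week 8: "Participants requiring rescue therapy after the Week 8 visit will be discontinued and an early withdrawal visit scheduled".
- Two weeks of hemoglobin censoring is stated for transfusion, prednisone/prednisolone rescue and dexamethasone rescue only.

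**Concomitant medication.** Section 7.9 refers sites to Sections 6.2 and 6.3 and to a study manual, and does not mention 6.9.2.

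**Scoring.** A Week 13 responder (Protocol Section 4, repeated in SAP Section 2.2.1) needs Hb of at least 10 g/dL, a rise of at least 2 g/dL, and no rescue or transfusion in the preceding two weeks. Section 10.3.2 analyses the ITT population on available data with no imputation. Withdrawal for concomitant-medication violations is discretionary under Section 6.7.1: "A Principal Investigator may discontinue/withdraw a participant from the study if any of the following criteria apply".

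**The concern.** A site that follows the note could treat a falling hemoglobin by local practice and go outside Section 6.9.2. That would be a deviation, but the protocol attaches no scoring consequence to it. If the agent acts for longer than two weeks, a hemoglobin rise that may be due to it could be credited to RVT-1401. There is no untreated control against which to judge how much of the rise belongs to the study drug. Section 3.3.1 says the results are meant to inform dosing and support a Phase 3 study.

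The outcome would also depend on the investigator's choice. For the same deviation, a participant kept on study can count as a responder, while one withdrawn before Week 13 has no Week 13 value and drops out of the proportion.

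**Working it through.** The plan gives no figure to reproduce: the sample size was not set statistically (Section 10.1). The check compares the texts and works through the visit calendar.

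**1. Which safeguard would change responder status after a non-permitted therapy completed by Week 8?**

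| Rule | Reach |
|---|---|
| Responder look-back (Section 4) | two weeks before Week 13 only |
| Hemoglobin censoring (6.9.2) | two weeks; three permitted rescue types only |
| Mandatory discontinuation (6.9.2) | rescue after the Week 8 visit only |
| Withdrawal for non-compliance (6.7.1) | optional; no link to response |
| Analysis populations (10.2.1) | ITT, Safety, PK and PD; none excludes for a deviation |

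None of these reaches the case.

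**2. Calendar.** Visits are weekly from Day 1 (Section 5.1), so day = 1 + 7 × (week − 1). The windows come from the Time and Events Table.
- Week 8: 1 + 49 = Day 50 (±1: 49 to 51).
- Week 13: 1 + 84 = Day 85 (±2: 83 to 87).
- Gap: 85 − 50 = 35 days. Shortest 83 − 51 = 32; longest 87 − 49 = 38.
- Beyond the 14-day look-back: 35 − 14 = 21 days, range 18 to 24.
- The look-back opens on Day 85 − 14 = 71. Nominally, Days 71 to 85 fall under the look-back and Days 51 to 70 under the post-Week 8 discontinuation rule. Days 1 to 50 fall under neither.

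**3. Comparison with the protocol's own washouts.** Section 6.3 excludes IVIG or plasma exchange within 60 days before Screening (criterion 4) and rituximab within 3 months before it (criterion 3). Applied backwards from Week 13 as a yardstick:
- IVIG or plasma exchange: 85 − 60 = Day 25, so use from Day 25 to Day 50 lies inside the 60 days.
- Rituximab: Day 1 is 85 − 1 = 84 days before Week 13, so any use from Day 1 lies inside 3 months (taken as about 90 days).

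**4. Size of one misclassified participant (100/n points).** The documents give about 16 participants but no split.
- Cohort of 8 (equal split assumed): 100/8 = 12.5 points.
- Cohorts of 10 to 6: 10 to 16.7 points.
- All 16 pooled: 6.25 points.
- Illustration for the planned Fisher's exact test at an assumed 8 versus 8: 6 versus 1 responders gives p = 0.041; 5 versus 1 gives p = 0.119.

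**The case against.** **Section 6.9.2 governs.** Sections 6.9.1 and 6.9.3 refer to it, criterion 9 is a closed list, and Section 8 allows no waivers except for immediate safety concerns. Section 7.9 also leads to exclusions that name rituximab, IVIG and plasma exchange. This stands. A reader might infer that the note authorises any locally accepted rescue; taken as a whole, the protocol does not support that. The note is loose wording, not a competing rule.

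**Much of the period is already covered.** The look-back refers to rescue in general, and rescue needed after Week 8 leads to discontinuation. A daily immunosuppressant or raised steroid dose that continues past Week 8 is therefore arguably caught. This also stands. The gap is for therapy finished by about Week 8 whose effect may last.

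**A case would be visible.** Concomitant medication is recorded with dose, dates and reason (Section 7.9) at every visit, starting rescue requires notice to the medical monitor (Section 6.9.3), and SAP Section 9.4 lists rescue and concomitant medication. A reader might infer that the problem would go undetected; it would not. Seeing a case is still different from having a rule for scoring it.

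**Other sources were not available.** The study manual may restrict agents. SAP Version 3.0 removed derived variables, so its silence reflects the move to listings; earlier versions may have had a responder derivation. This limits the claim to the protocol and SAP as supplied.

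**Two weeks is a chosen look-back.** It is, and permitted rescue escapes it too: a 5-day prednisone course started on Day 50 ends on Day 54, 85 − 54 = 31 days before Week 13. That is a stated endpoint choice and is not disputed here. It does not carry over to agents for which the protocol requires 60 days to 3 months before Screening.

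**Conclusion.** The point holds in a narrow form and with low severity. The inclusion 9 note is looser than the governing Section 6.9.2. As written, the two-week look-back would score as a responder a participant who completed rituximab, IVIG or plasma exchange by about Week 8, 35 days (32 to 38) before Week 13, provided the hemoglobin criteria are met and the participant stays on study.

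This rests on three assumptions: weekly visits as scheduled, the eligibility washouts as a fair yardstick for lasting effect (the protocol does not use them for scoring), and an equal split for the 12.5-point figure. The documents do not show how often such a case would arise.

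A reader might infer that reported results are biased. The documents do not support that. SAP Version 3.0 presents listings only and calculates no proportion; at the pause, 5 subjects were enrolled in Cohort 1, of whom 2 had completed through Week 20. The point concerns the proportion planned in the protocol.

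**What to change.** 1. End the inclusion 9 note with: *except for rescue therapy as permitted in Section 6.9.2*. Add 6.9.2 to the cross-reference in Section 7.9.
2. Add to the responder definition in Protocol Section 4, and wherever it is repeated: *A participant who between Day 1 and Week 13 receives rituximab, IVIG, plasma exchange, a new immunosuppressant or any other WAIHA therapy not permitted by Section 6.9.2, or whose background WAIHA dose is raised beyond the 6.9.2 dose limit or for more than 7 days, or who is discontinued for rescue after Week 8, is a non-responder at Week 13 and stays in the denominator.*

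The 7 days is a proposed tolerance for brief overruns of the 5-day prednisone limit and should be fixed in advance. Hemoglobin values are kept and flagged. The denominator wording is needed because Section 10.3.2 uses available data without imputation, so a withdrawn participant would otherwise leave the proportion. Naming post-Week 8 discontinuation treats those participants in the same way.

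Cost: one note, one cross-reference and one sentence. The sentence changes the primary endpoint, so it needs a protocol amendment with IRB/IEC approval (Section 13.1.2). The data are already collected, and the rule does not prevent clinically needed treatment. The downside is a possibly slightly lower response rate.
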